7.2 General Methodology

Continuous variables will be summarized using counts, means, 95% Agresti-Coull Confidence Intervals, standard deviations, medians, minimum and maximum.

Categorical variables will be summarized using frequencies and percentages.

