13.1. Statistical Test Methods

Continuous variables will be summarized using counts, means, standard deviations, medians, minimum and maximum. Categorical variables will be summarized using frequencies and percentages. Changes to the planned statistical analysis as defined in the protocol will be documented in the statistical analysis plan and clinical study report.

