13.4.2. Secondary Endpoints

To assess procedure details, operative time and intra-operative bleeding volume a sample value and margin of error (95% confidence level) will be calculated.

Incidence of post-operative hemorrhage, and post-operative readmission will be summarized using frequency and percentages.

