Subjects will receive at least nine copies of the VAS scale (below) where the lines are printed exactly 10cm in length. Prior to the subject receiving the scale, the subject ID will be written on the pages. On post-operative days 1 through 7, 10 and 14, each day the subjects will be instructed to place a vertical mark on the line, along with the date and time, to indicate their degree of pain. Rulers will be provided to each site and after their return on post-operative day 14 (+3), the vertical marks will be rounded to the nearest whole centimeter and entered into the eCRF. Marks which fall directly between two whole numbers will be rounded to the larger number; *i.e.* 3.5 would be rounded to 4.

17.3.APPENDIX C: List of Investigators and Institutions

Investigator	Institution Address
[name], MD	University of Texas Health Science Center – Houston Memorial Hermann [name] USA
[name], MD, PhD	Sophiahemmet Hospital ENT Department [name] Sweden

18. Version History

Version	Summary of Changes	Author(s)/Title
1.0	
 New Document 	[name]. Senior Medical Writer, Scientific Communications
1.1	
 Sections reordered per CIP template 056-F275 (Table of Contents) 	[name]. Senior Medical Writer, Scientific Communications
1.1	
 Local Sponsor for EU CAE added and Coordinating Investigator removed from Clinical Investigation Plan cover page 	[name]. Senior Medical Writer, Scientific Communications
1.1	
 Added ISO 14155:2011 and location specificity to Investigator Statement (Section 2) 	[name]. Senior Medical Writer, Scientific Communications
1.1	
 Updated Primary Objective and added Post-market interventional to Clinical Study Type, Primary Endpoint, Secondary Endpoints and Secondary Objectives to Synopsis (Section 4). 	[name]. Senior Medical Writer, Scientific Communications
1.1	
 Sample size revised to “a minimum of 48” throughout document 	[name]. Senior Medical Writer, Scientific Communications
1.1	
 Updated the definition of Hemostasis in the Glossary (Section 3) 	[name]. Senior Medical Writer, Scientific Communications

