7.7 Treatment Characteristics

The Study Investigator should perform the surgical procedure according to the appropriate standard procedures and practices at his/her institution using BiZact™. Additionally, the following procedures and assessments will be performed:

- Type of admission
- Adverse Events/Serious Adverse Events assessment
- Intra-operative bleeding volume
 - Record volume of any irrigant used
 - Record presence of gastric fluids
 - Record amount of fluid in suction container prior to stomach drainage
- Surgical performance parameters
 - Surgical technique
 - Operation time
 - Device ease of use
 - Dissection assessment
 - Other alternative devices used (if any)
 - Operation time used
 - Side
 - Reason for use
 - Tonsil size measurement (Measured via water displacement)
 - Using a graduated container that has 1mL markings, fill container to half full with water note mL level. Put the first tonsil into the water and record the mL level. The difference equals the volume of the first tonsil. Remove the first tonsil and note

This document is electronically controlled. Printed copies are considered uncontrolled.

Confidential

water level. Put the second tonsil into the water and record how much the water level rises. The difference equals the volume of the second tonsil.

- Concomitant medications - medications used during procedure, used for Averse Events and used for the treatment of pain (including but not limited to analgesics, anti-inflammatories, etc.)

Surgical procedure data will be summarized on the FAS and reported using statistical methods described above (see section 7.2 General Methodology).

This document is electronically controlled. Printed copies are considered uncontrolled.

Confidential

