Speech problems	HNSP	3	3	16, 23, 24
Trouble with social eating	HNSO	4	3	19-22
Trouble with social contact	HNSC	5	3	18, 25-28
Less sexuality	HNSX	2	3	29,30
Teeth	HNTE	1	3	9
Opening mouth	HNOM	1	3	10
Dry mouth	HNDR	1	3	11
Sticky saliva	HNSS	1	3	12
Coughing	HNCO	1	3	15
Felt ill	HNFI	1	3	17
Pain killers	HNPk	1	1	31
Nutritional supplements	HNNu	1	1	32
Feeding tube	HNFE	1	1	33
Weight loss	HNWL	1	1	34
Weight gain	HNWG	1	1	35

* Item range is the difference between the possible maximum and the minimum response to individual items.

Example:

Pain

$$\text{RawScore} = (Q1 + Q2 + Q3 + Q4)/4$$

$$\text{Pain Score} = \{(\text{RawScore}-1)/\text{Item range}\} * 100$$

Questions scores

Not at all = 1

No = 1

A little = 2

Yes = 2

Quite a bit = 3

Very much = 4

This document is electronically controlled. Printed copies are considered uncontrolled.

Confidential

- The incidence of patients having a post-operative hemorrhage, primary and secondary bleeding, and post-operative readmission along the follow-up will be assessed.
- Intra-operative bleeding, irrigant volumes and operative time will be calculated (counts, means, standard deviations, medians, minimum and maximum).

Secondary objectives will be run on both FAS and PPAS.

This document is electronically controlled. Printed copies are considered uncontrolled.

Confidential

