7.12 Changes to Planned Analysis

Analysis corresponds to the planned analysis in the CIP. Any deviations from this statistical plan will be justified in future revisions to this document or in the final report, as appropriate.

8 Validation Requirements

Level I validation will be performed for all the analysis output. Level I is defined as that the peer reviewer independently programs output and then compares the output with that generated by the original Statistical Programmer.

This document is electronically controlled. Printed copies are considered uncontrolled.

Confidential

9 References

10 Statistical Appendices

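### SAP 7.2 gives continuous variables Agresti-Coull intervals, a method for binomial proportions, so the 95% margin of error planned in CIP 13.4.2 has no valid named method

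*Combined protocol and SAP*

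**What the plan says.** SAP 7.2 (General Methodology) sets the summary rule for all continuous variables: "Continuous variables will be summarized using counts, means, 95% Agresti-Coull Confidence Intervals, standard deviations, medians, minimum and maximum". For the other variable type it says only: "Categorical variables will be summarized using frequencies and percentages". The SAP version history records the Agresti-Coull interval as an addition in version 3, and the sentence is identical in both copies of the SAP in the file.

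Other SAP sections depend on this rule. Section 7.6 refers baseline data to it. Section 7.7, whose list includes operation time and intra-operative bleeding volume, does the same: "Surgical procedure data will be summarized on the FAS and reported using statistical methods described above (see section 7.2 General Methodology".

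The CIP is different. Its general rule in 13.1 has no interval: "Continuous variables will be summarized using counts, means, standard deviations, medians, minimum and maximum". Its endpoint section, 13.4.2, does plan one, without a formula: for "operative time and intra-operative bleeding volume a sample value and margin of error (95% confidence level) will be calculated".

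SAP 7.9.2 covers the same endpoints with no interval: "Intra-operative bleeding, irrigant volumes and operative time will be calculated (counts, means, standard deviations, medians, minimum and maximum"). SAP 7.12 then states: "Analysis corresponds to the planned analysis in the CIP".

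**The concern.** The method named does not fit the data type it is assigned to. Agresti-Coull adjusts a count of successes and the number of trials, then uses the binomial variance p(1-p). A mean pain score, operative time or bleeding volume is not a proportion, and its precision depends on the sample SD, which the formula never uses.

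The rule reaches real outputs: the VAS means, the baseline and surgical tables, and the by-center summaries in SAP 7.3. It also leaves a CIP commitment without support. SAP 7.9.2 drops the margin of error for operative time and bleeding volume, and the only route to an interval elsewhere in the SAP text (7.7, then 7.2) leads to a method that is invalid for a mean. CIP 13.1 requires changes to the planned analysis to be documented in the SAP and the study report. SAP 7.12 records no change here.

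The study is single-arm and has no powered hypothesis, so estimates and their precision are its main product.

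**Working it through.** The plan gives no interval width, SD or sample-size calculation to reproduce. The check is whether the named formula can be applied, and what a valid one would give.

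**Inputs from the documents.** The minimum sample is 48 (CIP 13.2). The cap is 24 per site (CIP 8.2), which limits each center in the SAP 7.3 summaries. VAS lines are 10 cm long and "the vertical marks will be rounded to the nearest whole centimeter and entered into the eCRF" (CIP Appendix B).

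**Assumed inputs.** All means and SDs below are assumptions, because the documents give none.

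**Agresti-Coull formula.** With z = 1.96 and z² = 3.84:
- adjusted n: n~ = n + z²
- adjusted proportion: p~ = (x + z²/2) / n~
- half-width: z × √(p~(1 − p~) / n~)

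**Step 1: where the formula fails.** Putting a mean m in place of the proportion means x = n × m. The term p~(1 − p~) is negative when p~ > 1, that is, when m > 1 + z²/(2n).
- n = 48: 1 + 3.84/96 = 1.04
- n = 24: 1 + 3.84/48 = 1.08

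**Step 2: assumed means above the threshold, n = 48, n~ = 51.84.**

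| Assumed mean | p~ | p~(1 − p~) | Interval |
|---|---|---|---|
| VAS 2 cm | (96 + 1.92)/51.84 = 1.889 | −1.68 | none |
| VAS 5 cm | (240 + 1.92)/51.84 = 4.667 | −17.11 | none |
| Operative time 20 min | (960 + 1.92)/51.84 = 18.56 | −325.7 | none |

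**Step 3: an assumed mean below the threshold.** For a VAS mean of 0.5 cm, p~ = (24 + 1.92)/51.84 = 0.5. The half-width is 1.96 × √(0.25/51.84) = 0.136 cm, whatever the SD. The t-based half-width is t(0.975, 47) × SD/√48 = 2.012 × SD/6.928 = 0.290 × SD.

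| Assumed SD (cm) | t half-width (cm) | Agresti-Coull as a share of t |
|---|---|---|
| 0.5 | 0.145 | 0.136/0.145 = 94% |
| 1.0 | 0.290 | 0.136/0.290 = 47% |
| 1.5 | 0.436 | 0.136/0.436 = 31% |

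With whole-centimetre scores, a mean of 0.5 has its smallest SD, about 0.5, when half the scores are 0 and half are 1. The 94% is therefore the best case for that mean.

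**Step 4: what a valid margin would be.** The t-based margin at n = 48 is 0.290 × SD. For operative time with an assumed SD of 5 to 10 min, that is ±1.45 to ±2.90 min. For one full site (n = 24, t = 2.069) the multiplier is 2.069/√24 = 0.422.

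**Step 5: where the method does apply.** For 0 hemorrhages in 48, p~ = 1.92/51.84 = 0.037 and the upper limit is 8.8%. For 2 in 48 (4.2%), p~ = 3.92/51.84 = 0.0756 and the interval is 0.4% to 14.8%. The formula works for counts; the fault lies in attaching it to continuous variables.

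**The case against.** The strongest case on the other side accepts that the method is wrong for means and disputes how much follows from that.

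- **The CIP gap is separate.** SAP 7.9.2 would omit the interval for operative time and bleeding volume even if 7.2 were correct. This stands: there are two drafting faults. They meet because 7.2, reached through 7.7, is the only place in the SAP text that could supply the missing margin.
- **The margin can still be computed.** The SAP plans the count, mean and SD, which are all that a t interval needs. This stands too. The exact claim is that no valid method is named, not that the data are lacking.
- **The CIP is not uniform.** Its synopsis promises only a sample value for these two endpoints, and 13.1 and 13.2 list no interval. That is true, but 13.4.2 is the endpoint analysis section and it does plan one.
- **The table shells are in a separate file.** They might show a different interval, and this cannot be checked. Shells that did so would contradict SAP 7.2 as written.
- **The error would surface.** A negative variance gives a failed or blank cell, and SAP section 8 requires independent programming of all output. Detection is likely, but each programmer would then have to choose a method that the plan does not contain. The case that would pass unnoticed needs a mean below about 1.04.
- **The t interval is not always right either.** Strongly skewed scores near zero may call for a bootstrap. This is fair, and it qualifies the widths in the working but not the fault.
- **Nothing is decided on an interval.** The study is descriptive, with no success criterion that rests on one. This limits the impact but does not make the rule correct.

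**Conclusion.** The concern holds. SAP 7.2 states a rule that gives either no interval or a wrong one for continuous variables, and the margin of error planned in CIP 13.4.2 has no valid named method in the SAP. The thresholds of 1.04 (n = 48) and 1.08 (n = 24) follow from the formula and the documents' own sample sizes. The other widths for continuous variables rest on assumed means and SDs, and the t comparison assumes that a t interval is adequate for the data.

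The damage is confined to intervals. Point estimates, SDs, percentages and the Friedman tests in SAP 7.9.1 and 7.9.2 do not change. That the interval was meant for the categorical line is plausible but is not stated in either document. The absence of an interval for hemorrhage and readmission is an omission consistent with the CIP, not a contradiction. This should be fixed before analysis, but it does not threaten the study's main results.

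**What to change.** 1. In SAP 7.2, replace the Agresti-Coull interval for continuous variables with a t-based 95% confidence interval for the mean. A bootstrap interval can be named for clearly skewed variables.
2. In SAP 7.9.2, add that 95% interval for operative time and intra-operative bleeding volume, so that the section matches CIP 13.4.2 and the statement in 7.12 becomes true on this point.
3. Optionally, move the Agresti-Coull (or Wilson) 95% interval to the categorical line of 7.2 and report it beside the hemorrhage and readmission percentages in 7.9.2.
4. Check that the separate table shells carry the same intervals.

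The cost is two lines in SAP 7.2, one in 7.9.2 and trivial programming. No new data are needed.

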7.3 Center Pooling

Subgroup analyses for primary and secondary endpoints will be presented by clinical center.

This document is electronically controlled. Printed copies are considered uncontrolled.

Confidential

7.4 Handling of Missing Data and Dropouts

No method of imputation will be used for missing data. A summary of missing data will be provided according to the number of subjects, the time points where the data are missing and clinical center. For each clinical center, number and percent of subjects with no missing data will be presented in tabular form.

7.5 Adjustments for Multiple Comparisons

Only one analysis will be performed then no adjustment for multiple comparison will be performed.

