
Study Procedures and Assessments
	
Pre-operative & Operative Assessments:
 
 • Histories: Medical, Surgical, Medication • Urine Pregnancy test for females of child bearing potential (US only) • Intra-operative bleeding volume-volume of stomach juices and blood should be measured prior to stomach draining • Irrigant volume – volume to be recorded of operative field irrigant used during procedure • Operative time-time from the first incision to complete hemostasis of the tonsillar bed (excluding closing time) • Subjects will be followed for 2 weeks post tonsillectomy procedure. 
Follow-up Assessments (Form filled out by subject on post-operative days 1-7, 10 and 14):
 
 • Pain level • Analgesic consumption • Ability to return to normal diet • Ability to return to normal activity • Incidence of post-operative hemorrhage - any primary (≤ 24 hrs) and secondary (> 24 hrs) bleeding • Incidence of post-operative readmission

Safety Assessments
	
 • Adverse events (AEs), Serious Adverse Events (SAEs), Adverse device effects (ADE) and Unanticipated serious adverse device effects (USADE) • Device deficiencies • Focal Infection

Statistics
	
 • Pain levels will be captured at post-operative days 1-7, 10, and 14 for each subject. Paired tests may be used to test whether there is a mean change along the follow-up. • For operative time and intra-operative bleeding volume a sample value will be calculated. Incidence of post-operative

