13.4. Statistical Analysis of Endpoints

13.4.1. Primary Endpoint

To assess pain, pain levels will be captured at post-operative days 1-7, 10, and 14 for each subject using the VAS. For each defined post-operative time point, paired tests will be used to test whether there is a mean change along the follow-up.

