7.9 Evaluation of Objectives

7.9.1 Primary objective

The severity of pain will be analyzed at each post-operative assessment: at days 1 through 7, 10 and 14. This pain score will be assessed quantitatively using the VAS scale and qualitatively using the below subgroups:

- No Pain: VAS= 0
- Mild Pain: VAS > 0 and < 4
- Moderate: VAS ≥ 4 and < 7
- Severe: VAS ≥ 7

Friedman's test will be performed so as to assess the distribution of the VAS along the follow-up and testing whether the VAS per visits are from a same population:

- H_0 : $M_1 = M_2 = M_3 = M_4 = M_5 = M_6 = M_7 = M_{10} = M_{14}$ (the distribution of the VAS is the same in all timepoints)
- H_a : There is at least one pair (i,j) such as $M_i \neq M_j$.

Subgroup analyses will be performed according to the use of pain killers.

Primary objective analysis will be run on both FAS and PPAS.

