7.9.2 Secondary objectives

- The incidence of patients with analgesic consumption will be assessed at each timepoint and globally using frequency and percentages. On the whole follow-up the total consumption of analgesics (narcotics and non-narcotics analgesics) will be assessed. Patients with analgesics will be identified based on dosing diary.
- Ability to return to normal diet and normal activity and patients quality of life after operation will be presented:
 - Calculating the time (counts, means, standard deviations, medians, minimum and maximum) between the operation and the return to normal diet or activity dates.
 - Calculating the incidence of patients being returned to normal diet or activity after operation.
 - Using the **EORTC QLQ-H&N35 questionnaire**:

The head & neck cancer module is meant for use among a wide range of patients with head & neck cancer, varying in disease stage and treatment modality (i.e. surgery, radiotherapy and chemotherapy) (Bjordal and Kaasa, 1992; Bjordal et al., 1994, 1999, 2000) (1-3). The module comprises 35 questions assessing symptoms and side effects of treatment, social function and body image/sexuality. The module has been

This document is electronically controlled. Printed copies are considered uncontrolled.

Confidential

developed according to the guidelines, and pretested on patients from Norway, Sweden, Denmark, the UK and French-speaking Belgium. It has been field tested in Norway, Sweden and The Netherlands, and in a large cross-cultural study involving more than ten countries (EORTC Protocol 15941).

Scoring of the head & neck cancer module

The head & neck cancer module incorporates seven multi-item scales that assess pain, swallowing, senses (taste and smell), speech, social eating, social contact and sexuality. There are also eleven single items. **For all items and scales, high scores indicate more problems** (i.e. there are no function scales in which high scores would mean better functioning).

Friedman's test will be applied to assess the distribution of the scores along the follow-up timepoint:

- $H_0: M_1 = M_2 = M_3 = M_4 = M_5 = M_6 = M_7 = M_{10} = M_{14}$ (The distribution of the Symptom score is the same in all timepoints)
- H_a : There is at least one pair (i,j) such as $M_i \neq M_j$.

Scale name	Scale	Number of items	Item range*	QLQ-H&N35 Item numbers
Symptom scales / items				
Pain	HNPA	4	3	1-4
Swallowing	HNSW	4	3	5-8
Senses problems	HNSE	2	3	13, 14

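### SAP 7.5 waives multiplicity adjustment because only one analysis is planned, but SAP 7.9 plans up to 19 (or 14) main Friedman tests per analysis set

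*Combined protocol and SAP*

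**What the plan says.** - SAP 7.5 (Adjustments for Multiple Comparisons) consists of one sentence: "Only one analysis will be performed then no adjustment for multiple comparison will be performed".
- SAP 7.9.1 plans a Friedman test on the primary endpoint: "test will be performed so as to assess the distribution of the VAS along the follow-up". It covers nine timepoints (days 1 to 7, 10 and 14), is run on FAS and PPAS, and has subgroup analyses by pain-killer use.
- SAP 7.9.2 plans the same test for the questionnaire: "test will be applied to assess the distribution of the scores along the follow-up timepoint". It describes seven multi-item scales and adds: "There are also eleven single items". It closes with: "Secondary objectives will be run on both FAS and PPAS".
- SAP 7.3 adds subgroup presentation by center for primary and secondary endpoints. SAP 7.8 separately rules out interim analyses.
- SAP 7.12 states: "Analysis corresponds to the planned analysis in the CIP". For the VAS, however, CIP 13.4.1 says: "paired tests will be used to test whether there is a mean change along the follow-up". The Statistics row of the CIP synopsis is looser: "Paired tests may be used to test whether there is a mean change along the follow-up". CIP 13.1 requires changes from the protocol analysis to be documented in the SAP and the study report.
- SAP 6 and CIP 13.2 describe a study without a powered hypothesis, summarised descriptively.

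**The concern.** The stated ground for not adjusting is a count, and the count does not match the analyses two pages later. SAP 7.9 sets out formal null and alternative hypotheses for the VAS and for the questionnaire scores. SAP 4.2 calls the secondary objectives hypotheses. Nothing labels the resulting p-values exploratory.

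What is at stake is interpretation. The CIP intends publication. A reader of the results could describe individual QLQ-H&N35 scores as changed over follow-up on the strength of unadjusted p-values, believing from SAP 7.5 that multiplicity did not arise.

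Two smaller gaps are linked to this. SAP 7.12 declares agreement with the CIP although the test on the primary endpoint differs. In addition, a standard Friedman test without imputation uses only subjects with all nine scores, and no text ties that number to the test.

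**Working it through.** **Step 1. Try to reproduce the plan's figure of one.** It can be reached in two ways only: by counting the VAS test alone, in one analysis set and without subgroups, or by reading one analysis as one look at the data. The VAS test in FAS and PPAS already makes two.

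**Step 2. Count the tests in SAP 7.9.** The inputs are the SAP 7.9.2 text and scoring table.
- Multi-item scales: 7, with 4 + 4 + 2 + 3 + 4 + 5 + 2 = 24 items.
- Single items: 11. Total items 24 + 11 = 35, each used once, so table and text agree.
- Scores: 7 + 11 = 18. Five have item range 1, meaning yes/no (items 31 to 35 in the SAP table, 61 to 65 on the form). Without them, 18 − 5 = 13.
- Adding the VAS: 18 + 1 = 19, or 13 + 1 = 14 per set. Over FAS and PPAS: 38 or 28, although the sets overlap because PPAS is a subset of FAS.

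The SAP does not list which scores are tested, and its null hypothesis refers to the symptom score in the singular, so these counts are given as up to 19 or 14. Even one VAS test plus one score test exceeds one. Tests within pain-killer or center subgroups, if run, would come on top.

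**Step 3. Illustrate the size.** No alpha is stated; 0.05 is assumed. With m independent tests, all nulls true and each test at its nominal level, P(at least one false positive) = 1 − 0.95^m.

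| True nulls m | Meaning | Probability |
|---|---|---|
| 19 | VAS + 18 scores | 62% |
| 18 | 18 scores only | 60% |
| 14 | VAS + 13 scores | 51% |
| 13 | 13 scores only | 49% |
| 5 | only five nulls true | 23% |

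**Step 4. Vary the assumptions.**
- *Correlation between scores lowers it.* Simulation with 48 subjects, nine independent days and normal scores (4,000 runs): at correlations 0.3, 0.5 and 0.7 the figure is 54%, 47% and 36% for 19 tests, and 45%, 40% and 31% for 14.
- *Correlation between days raises it.* The Friedman reference distribution treats a subject's days as exchangeable under the null. The questionnaire asks about the past week (CIP Appendix A) and is completed daily on days 1 to 7, so the recall windows overlap. With an assumed day-to-day correlation of 0.5 to 0.9, decaying with the gap between days, simulation gives a per-test error of about 6 to 8% and up to 78% for any false positive over 18 scores.
- *Holm across the 18 scores* starts at 0.05/18 = 0.0028 (0.05/13 = 0.0038 for 13). It keeps the error below 5% when days are independent, but leaves about 6 to 23% under the serial correlation just described.

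**Step 5. Compare CIP and SAP on the primary test.** CIP 13.4.1 specifies paired tests of mean change. SAP 7.9.1 specifies one omnibus rank test of equal distributions. The hypotheses differ, and nine timepoints give 9 × 8/2 = 36 possible pairs, or 8 comparisons with day 1. SAP 7.12 records no difference.

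**Step 6. Complete VAS series.** The missing rate q per form is assumed. Out of 48 subjects, complete series number from 48 × (1 − q)^9 (independent misses) to 48 × (1 − q) (fully clustered): 40 to 47 at 2%, 30 to 46 at 5%, 19 to 43 at 10%.

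**The case against.** The strongest defence is that the study is descriptive and unpowered, so unadjusted p-values need no defence. This stands as far as it goes: unadjusted exploratory p-values are acceptable. But SAP 7.5 does not give that reason, and no section supplies the label.

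A second defence reads one analysis as one data look. SAP 7.8 already says that, and 7.5 is headed multiple comparisons, so the several tests would remain unaddressed.

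Third, all nulls being true is remote after tonsillectomy: pain, swallowing and eating scores should change, and a feeding-tube item may be constant. This stands; the case with five true nulls (23%) shows its effect.

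On the CIP mismatch, the synopsis makes paired tests optional, CIP 13.2 defers detail to the SAP, the Friedman test is itself a related-samples test, and the SAP version history records a revision to the primary endpoint process. A reader might infer an undisclosed switch of the primary analysis. The documents do not support that: they do not show which text changed, and the CIP history also records a clarification of the tests. What remains is a documentation correction under CIP 13.1.

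On complete cases, SAP 7.1.1 and 7.4 already report completions and subjects without missing data, and the table shells, kept in a separate file, may print the number used and list the tested scores. This makes the point secondary.

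**Conclusion.** The reason given in SAP 7.5 is wrong as written: SAP 7.9 plans up to 19 main tests per analysis set, or 14 without the yes/no items, on both FAS and PPAS. The 62% and 51% figures are illustrations resting on an assumed alpha of 0.05, all nulls true, and independent scores and days.

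Three stronger readings are tempting and should be avoided. First, 62% is not an upper bound, because serial correlation between days can push the error higher. Second, 19 is not a ceiling on the number of tests, because SAP 7.3 and 7.9.1 allow subgroup analyses. Third, Holm does not guarantee 5%, because it needs each Friedman p-value to be valid, which overlapping recall windows can break.

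Nor is the primary result undermined: no confirmatory claim, sample size or design feature depends on this. The SAP 7.12 statement needs correcting as a matter of record, and the complete-case number is a reporting addition. The point should be fixed before analysis, and the change is small.

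**What to change.** **SAP 7.5.** Delete the reason based on one analysis. State that:
- the VAS Friedman test on the FAS is the single primary test;
- all p-values are exploratory;
- the QLQ-H&N35 scores to be tested, if any, are those named in the section.

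Then choose one of two options. Preferably, report the QLQ-H&N35 scores descriptively without p-values. Otherwise, apply Holm across the named scores, with a note that nominal control assumes valid Friedman p-values and that serial correlation between days can break this.

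**SAP 7.12.** Replace the statement of correspondence with one saying, with the reason, that an omnibus Friedman test is used in place of the paired tests of mean change in CIP 13.4.1, which the synopsis presents as optional.

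**SAP 7.9.1.** Print the number of subjects with all nine VAS scores beside the Friedman p-value. A sensitivity test using all observed scores, such as Skillings-Mack, is optional; it still assumes that missingness is unrelated to the unobserved scores.

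**Cost.** Wording in two sections and one printed number. Design, data collection and the primary test are unchanged.
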